### **9.5. Subgroup Analyses**

Subgroups of interest include:

- Age (<65 versus  $\geq 65$  years)
- Gender
- Any post-baseline LDL-C  $< 25$  mg/dL
- HIV status, CD4+ T-cell count above and below the median, specific antiretroviral therapy
- HCV status
- Triglyceride, Lp(a), PCSK9, hs-CRP, IL-6, fibrinogen, sCD14, sCD163 and D-dimer levels above versus below the median.

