### **1.2.2. Bococizumab**

Bococizumab (RN316/PF-04950615) is a novel humanized PCSK9 monoclonal antibody targeting the evolutionarily conserved LDL receptor-binding domain of PCSK9 with high affinity. The constant region of bococizumab is based on the human IgG2 isotype bearing two amino acid mutations, called IgG2 $\Delta$ a, which have greatly reduced ability to bind to Fc $\gamma$  receptors or fix complement. In nonclinical models, PF-04950615 binds to secreted PCSK9, effectively prevents PCSK9 from degrading LDLR, leading to improved LDL-C clearance in plasma and reduction of circulating LDL-C.

In a 24-week, multicenter, randomized, double-blind, placebo-controlled phase II trial, the LDL-C lowering effects of bococizumab, administered every 2 or 4 weeks in statin-treated adults with LDL-C  $\geq 80$  mg/dL was assessed. Subjects were randomized to placebo, bococizumab 50 mg, 100 mg, or 150 mg every 2 weeks, or placebo, bococizumab 200 mg or 300 mg monthly. The dose was reduced if LDL-C was  $\leq 25$  mg/dL. The primary analysis was the placebo-adjusted treatment difference for the change from baseline in LDL-C at week 12.

Overall, 354 patients were randomized, 351 received study treatment, and 299 completed the study. Bococizumab significantly reduced LDL-C across all doses. The placebo-adjusted LDL-C reduction at 12 weeks for the 2-weekly dosing regimen was 34.3% with 50 mg, 45.1% for 100 mg and 53.4% for 150 mg, and for the monthly dosing regimen was 27.6% for 200 mg and 44.9% for 300 mg. The incidence and profile of adverse events were similar across placebo and bococizumab groups. The incidence of moderate and severe injection site reactions and of serious adverse events was low in all treatment groups.

As of 1 December 2013, a total of 517 subjects had received at least one dose of bococizumab in completed studies, administered either as single or multiple dose both alone and in combination with current lipid lowering agents; bococizumab was generally well tolerated. No subjects in completed studies had drug-induced liver injury according to the Hy's law definition. Thirty-seven subjects (7%) exposed to bococizumab across all completed studies developed anti-drug antibodies but none were associated with any clinical signs or symptoms of hypersensitivity.

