Based on the findings of the study described above, 150 mg every 2 weeks was selected as the dose for phase III trials, including this trial. Because multiple doses of bococizumab as high as 150 mg every 2 weeks and 300 mg every 4 weeks up to 12 weeks were safe and well tolerated, the primary rationale for dose selection was the pharmacokinetic/pharmacodynamic model that predicted LDL-C changes from baseline. Based on population PK/PD modeling, a dose of 150 mg every 2 weeks in patients on a background of statins is estimated to be equivalent to approximately 80% of the maximal response for LDL-C lowering (-67%). Assuming an average LDL-C at baseline of 100 mg/dL for HIV-infected individuals, the mean absolute LDL-C reduction is predicted to be approximately -60 mg/dL.

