#### **5. STUDY TREATMENTS**

Subjects will be randomized into one of 2 parallel groups:

- Bococizumab 150 mg subcutaneously every 2 weeks (n=100);
- Bococizumab placebo subcutaneously every 2 weeks (n=100);

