### **6.2.3. Visit Day 365/End of Study Visit (EOS) ( $\pm 3$ days)**

The following procedures apply to subjects attending for Visit Day 365 or an early discontinuation visit if subjects choose to discontinue participation before Day 365. As detailed in Subject Withdrawal (Section 6.4) every effort should be made to ensure that all subjects complete study participation. Subjects who discontinue study treatment will be encouraged to continue participation in the study and complete all protocol assessments/evaluations. If, however, subjects choose not to continue attending study visits subjects should be encouraged to attend an EOS Visit and the follow up visits if indicated.

Review results from laboratory values;

Measure and record vital signs: heart rate (HR), temperature and BP (Section 7.2.5);

Conduct 12-lead ECG test (Section 7.2.4);

Obtain and record on-going medications and instruct subjects on the use of concomitant medications (Section 5.5);

Inquire for and record adverse events;

Collect specimens for laboratory exams:

Provide lifestyle and contraception recommendations (Section 4.4.1);

Administer optional depression questionnaire;

Collect all used and unused pre-filled syringe cartons.

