### **9.1. Sample Size Determinations**

Approximately 200 subjects will be enrolled into the trial to provide comprehensive safety data for bococizumab in HIV-infected subjects. Sample size calculations indicate that smaller numbers are required to demonstrate efficacy for the main study endpoints.

The primary endpoint is percent change from baseline to week 12 in fasting LDL-C and the primary comparison of interest is bococizumab 150 mg compared to placebo.

Assuming a dropout rate of 10% for the first 3 months, 54 subjects per treatment group provide more than sufficient power ( $\geq 99\%$ ) to detect expected treatment differences based on the results of a previous study. These calculations are based on  $\alpha=0.05$  (two-sided), a common standard deviation of 25% (based on previous study results), and on

using the normal approximation of the test statistic for the comparison between two means.

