### **9.4. Safety Analysis**

Safety will be assessed through adverse and serious adverse events, vital signs, and physical examination, 12-lead ECG recordings, and safety laboratory tests including anti-drug antibodies, hematology, and blood chemistry studies. Unless otherwise specified, safety analyses will be done in the Safety Analysis Set, which is comprised of all subjects who have received at least one dose of randomized study medication. All summaries of safety data will be descriptive only, unless indicated otherwise.

UCSF CHR/HRPP guidelines will be utilized when reporting adverse events. Adverse events, adverse events leading to discontinuation from treatment, and serious adverse events will be tabulated by treatment group. Summaries will also be provided by severity and relationship to study therapy.

Mean observed and mean change from baseline in systolic blood pressure, diastolic blood pressure, heart rate, and weight will be tabulated by visit according to sponsor standards. Observations of potential clinical concern for these parameters will be tabulated according to sponsor standards. Height and temperature will be listed.

Mean observed and mean change from baseline in hematology and blood chemistry parameters will be tabulated by visit according to sponsor standards. Observations of potential clinical concern for hematology and blood chemistry parameters will be

tabulated by treatment group according to sponsor standards. In addition, the proportion of subjects with anti-drug antibodies will be tabulated by treatment group.

12-lead ECGs will be locally read and the interpretations will be kept at the investigation sites as source documents. Any clinically significant ECG abnormalities will be reported as adverse events. Physical examination findings will be listed.

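### Does listing a post-baseline LDL-C below 25 mg/dL as a subgroup in section 9.5 commit the trial to a biased comparison?

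*Combined protocol and SAP*

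**What the plan says.** Section 9.5 opens with "Subgroups of interest include" and continues as a plain list: age, gender, "Any post-baseline LDL-C" below 25 mg/dL, HIV and CD4 status with specific antiretroviral therapy, HCV status, and a set of laboratory markers split at the median. It gives no endpoint, analysis set, model or arm contrast for any item.

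Four other places bear on how the LDL-C item would be used.

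- Section 1.2.6 names a very low LDL-C as a possible added risk for those on active treatment, of unknown consequence.
- Section 7.1.1 sends subjects with LDL-C at or below 25 mg/dL to the data monitoring committee.
- Section 9.4 states: "All summaries of safety data will be descriptive only, unless indicated otherwise".
- Section 9 leaves detailed methods to a SAP. The supplied text contains no SAP wording on subgroups.

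The efficacy analyses are set out in sections 9.2 to 9.2.6. The primary set is all randomised subjects, analysed by randomised arm, with a mixed model for repeated measures for the lipid change endpoints. None of these sections mentions the LDL-C below 25 group.

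**The concern.** Most of the list consists of characteristics a subject brings to randomisation. This item does not: it is decided by LDL-C during treatment, and the drug is given to lower LDL-C. Comparing arms within a group defined by response to treatment gives up the balance that randomisation provides. The subjects with the largest falls leave the complement, and they leave it from the active arm only, so a constant treatment effect would appear weaker there. In the below-25 group there would be almost no placebo subjects to compare with.

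Because the item shares a list with age and gender, a reader could suppose it will get the same treatment-by-subgroup analysis. If that were done on LDL-C or another efficacy endpoint, the trial could report effect modification where none exists.

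**Working it through.** **Inputs from the protocol.** Section 1.2.2: "Assuming an average LDL-C at baseline of 100 mg/dL for HIV-infected individuals", and a placebo-adjusted reduction of "53.4% for 150 mg" every 2 weeks. Section 9.1: "a common standard deviation of 25% (based on previous study results" and 54 subjects per group. Section 5: "Bococizumab placebo subcutaneously every 2 weeks (n=100"), with the same number on bococizumab. Schedule of Activities: on-treatment lipid visits at weeks 4, 8, 12, 24, 30, 40 and 52.

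**Assumptions.** Placebo change 0; constant effect over all visits; within-subject correlation 0.5 to 0.9; no dropout; baseline either fixed at 100 or normal(100, 25) truncated at 70; SDs of 15 and 20 as alternatives to the plan's 25.

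**The plan's own power figure.** 53.4 / (25 × √(2/54)) = 53.4 / 4.81 = 11.1. Power is Φ(11.1 − 1.96), above 99.9%, which agrees with the stated 99% or more. Allowing for 10% dropout, 54 / 0.9 = 60 per group, as the Protocol Summary says.

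**Who would be in the group: one visit, normal model.** From 100 mg/dL, falling below 25 needs a drop of more than 75%.

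- Bococizumab: Φ((−75 + 53.4)/25) = Φ(−0.864) = 0.194.
- Placebo: Φ(−75/25) = Φ(−3) = 0.00135.

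That is about 19 against 0.1 per 100.

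**Who would be in the group: any of seven visits, simulated, SD 25.**

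- Normal: 32 to 54 per 100 on bococizumab against 0.4 to 0.9 on placebo, so 98.3% to 98.8% of members are on bococizumab.
- Log-normal LDL-C ratio with the same mean and SD: 27 to 48 per 100 against about 0.

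With SD 15 or 20 the placebo count is below 0.1 per 100 under either model. The imbalance therefore does not depend on the SD.

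**What an efficacy contrast in the complement would show** (week-12 percent change, true difference −53.4).

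One visit, normal, SD 25. The mean of a normal variable above a cut at a standard deviations is μ + σφ(a)/(1 − Φ(a)).

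- Bococizumab, a = −0.864: −53.4 + 8.5 = −44.9.
- Placebo, a = −3: 0 + 0.1 = 0.1.
- Difference: −45.0, which is 8.4 points too small.

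Any of seven visits, simulated:

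| SD | Log-normal: contrast | Too small by | Normal: contrast | Too small by |
|---|---|---|---|---|
| 25 (plan) | −41.7 to −45.4 | 8 to 12 | −38.8 to −41.4 | 12 to 15 |
| 20 (assumed) | −47.0 to −48.9 | about 5 to 6 | from −43.8 | 8 to 10 |
| 15 (assumed) | −51.1 to −51.7 | about 2 | from −48.7 | 4 to 5 |

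The log-normal column is the one to read. Under the normal model at SD 25, Φ((−100 + 53.4)/25) = Φ(−1.864) = 3.1% of bococizumab values at each visit correspond to a negative LDL-C. Over seven visits such subjects make up about 21% to 25% of the simulated group, which inflates the distortion.

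**Whether the plan runs that contrast.** Section 9.5 assigns no endpoint and no comparison. Sections 9.2 to 9.2.6 define every efficacy comparison without this group. The item counts any post-baseline visit, which suits a flag for exposure to very low LDL-C and does not match a week-12 endpoint. Sections 1.2.6 and 7.1.1 supply the safety motive, and section 9.4 makes safety summaries descriptive. Section 9.5 itself sits between the safety analysis (9.4) and the monitoring committee (9.6).

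**The case for a change.** The strongest case for a change is that nothing in section 9.5 confines this item to safety. Section 9.5 stands at the same level as 9.2 to 9.4 and does not refer back to 9.4, and section 9.4 never names the group. The monitoring rule in 7.1.1 is not an analysis rule. One sentence would settle the matter, and saying that treatment-effect subgroups use baseline values would also date the CD4 and marker median splits. The imbalance holds under every SD and distribution tried, so a reader who did take the list as a set of efficacy subgroups would be misled.

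Most of this stands as description. The use is unstated, the group is post-randomisation, and a clarifying sentence would do no harm. It does not show that any planned result is wrong. The objection is to an analysis the plan has not proposed. In the below-25 group such an analysis would fail visibly, with about zero or one placebo subject per 100. The complement contrast could be computed, but no section calls for it. A short subgroup list is ordinary in a protocol that leaves detail to a SAP, and a restriction there cannot be ruled out.

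For the likely safety use, one caution remains: a subject must stay under measurement long enough to be seen below 25. Section 6.2.3 partly meets it: "Subjects who discontinue study treatment will be encouraged to continue participation in the study and complete all protocol assessments/evaluations".

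**Conclusion.** No change to the plan follows. The item is a post-randomisation variable and nearly a proxy for arm: about 19% against 0.13% at one visit, and at least 98% of members on bococizumab in every case run. That would matter only if arms were contrasted on efficacy within it or its complement. The plan schedules no such contrast, and its own sections make a descriptive safety summary the natural reading. What is missing is a statement of use that a competent analyst would supply.

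The conditional distortion in the complement is about 2 to 12 points under the log-normal model (8 to 12 at the plan's SD of 25, 2 to 6 at assumed SDs of 15 to 20). It rests on the assumed placebo change of 0, constant effect, visit correlations and absence of dropout. It does not measure bias in adverse event summaries. The primary comparison in all randomised subjects, and the gatekeeping and Hochberg control in section 9.2, do not involve this group.

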### **3. STUDY DESIGN**

This study is a Phase 3, double blind, placebo-controlled, randomized, parallel group study, designed to compare the efficacy and safety of bococizumab 150 mg subcutaneously every 2 weeks to bococizumab placebo subcutaneously every 2 weeks for LDL-C lowering in HIV-infected subjects. The study will enroll approximately 200 subjects in 2 treatment arms, randomized 1:1 to either bococizumab or placebo injections. Randomized subjects will receive study drug for 52 weeks. Rates of discontinuation due to AEs and SAEs will be described for both treatment groups.

After providing informed consent at the screening visit, subjects will be assessed to determine eligibility for the trial. Eligible subjects will be considered enrolled and progress to the Baseline visit. Results from screening evaluations will be reviewed and only subjects who continue to meet all eligibility criteria will be randomized. Randomized subjects will enter the 52-week treatment period, followed by a 6-week follow-up, for a total of 58 weeks study participation. Subjects will attend clinic visits as shown in the Schedule of Activities. Lipid levels will be blinded to the investigator and staff, and subjects.

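### Section 9.5 groups ten continuous markers only by a split at the median; a continuous treatment-by-baseline-marker analysis would retain more information if modification is roughly linear

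*Combined protocol and SAP*

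**What the plan says.** Section 9.5 is a short list of subgroups. Its last bullet reads "Triglyceride, Lp(a), PCSK9, hs-CRP, IL-6, fibrinogen, sCD14, sCD163 and D-dimer levels above versus below the median", which covers nine continuous markers. A separate bullet adds a tenth: "HIV status, CD4+ T-cell count above and below the median, specific antiretroviral therapy". The section gives no numerical cut-point, endpoint, model or interaction test. It does not say whether the levels are baseline levels.

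Other sections use some of these markers for different questions. Sections 2.1.4 and 2.1.6 relate changes in most of them to changes in arterial inflammation or FMD. Section 9.2.6 enters current and nadir CD4 count as covariates in models for change in FMD. None of these asks whether the effect of bococizumab varies with the level of the marker.

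Section 9 defers detailed methods to the SAP. The combined document contains no separate SAP text on these subgroups, so the median grouping is the only specification available.

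**The concern.** A subgroup list is normally read as a search for differences in treatment effect. Replacing a continuous marker by a two-level indicator treats a subject just above the median like one at the top of the range. If the effect changes gradually with the marker, that removes information from a comparison that is weak to begin with: the trial was sized for safety and for the LDL-C main effect, not for interactions.

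Two smaller points come with it.

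- **Cut-points.** A sample median is not known until the sample is in, and it moves with who enrols. For hs-CRP the protocol already has a fixed threshold of 2 mg/L (section 4.1, criterion 7), which 9.5 does not use.
- **Timing.** The list does not date the marker values. Lp(a) is a key secondary endpoint (2.2.2) and change in PCSK9 an exploratory one (2.2.5). A split on values measured after treatment starts would partly sort subjects by arm.

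At stake is how much the trial can say about effect modification. The main efficacy result is not in question.

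**Working it through.** **Inputs from the documents**

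- Sample size and allocation (section 3): "The study will enroll approximately 200 subjects in 2 treatment arms, randomized 1:1 to either bococizumab or placebo injections". With the 10% dropout of section 9.1, 200 × 0.90 = 180 evaluable.
- Variability of percent change in LDL-C (9.1): "a common standard deviation of 25" percentage points. Alpha is 0.05, two-sided.
- Expected effect: 9.1 gives no number. The phase II results in 1.2.2 are "34.3% with 50 mg, 45.1% for 100 mg and 53.4% for 150 mg", so 53.4 points for the trial regimen.

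**Assumptions not in the documents:** the marker is normal (after log transformation where needed), the effect changes linearly by *b* percentage points per marker SD, and the residual SD is 25.

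**1. The plan's own figure.** Section 9.1 states that "54 subjects per treatment group provide more than sufficient power" (at least 99%). SE = 25 × √(2/54) = 4.81, and 53.4/4.81 = 11.1, so power exceeds 99.9%. It stays at or above 99% for any difference of about 21 points or more. 54/0.90 = 60 per group, as in the protocol summary. The figure reproduces, but it concerns the main effect. The documents give no power figure for subgroups.

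**2. Information kept by a median split.** For a linear trend, the relative efficiency is the squared correlation between the marker and its above-median indicator. For a normal marker this is 2/π = 0.637, a loss of 36%. For that trend, 180 subjects carry the information of 180 × 0.637 ≈ 115.

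| Shape of effect and marker | Information lost |
|---|---|
| Step exactly at the median | 0% |
| Linear, uniform marker | 25% |
| Linear, normal marker (or linear in the log of a lognormal) | 36% |
| Linear in the raw value, exponential marker | 52% |
| Linear in the raw value, lognormal, log-SD 0.4 to 1.0 | 44% to 73% |

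**3. Power of the treatment-by-marker test, N = 180**

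- Continuous: SE of *b* = 2 × 25/√180 = 3.73.
- Split: expected difference in treatment effect between halves = 2*b*√(2/π) = 1.596*b*, with SE = 4 × 25/√180 = 7.45.
- Power ≈ Φ(estimate/SE − 1.96). For *b* = 5, continuous: 5/3.73 = 1.34, Φ(−0.62) = 27%. Split: 7.98/7.45 = 1.07, Φ(−0.89) = 19%.

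| Slope *b* (points per SD) | Normal approximation: continuous vs split | Simulated t-test: continuous vs split |
|---|---|---|
| 5 | 27% vs 19% | 26% vs 18% |
| 8 | 57% vs 40% | about 56% vs 39% |
| 10 | 77% vs 57% | 75% vs 55% |

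Type I error per test is about 5% for both methods. The slope with 80% power when the marker is continuous is (1.96 + 0.84) × 3.73 = 10.4 points per SD; the split then has 61%. For the split to reach 80%, the two halves must differ by 2.80 × 7.45 = 20.9 points, about two-fifths of 53.4.

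**4. Stability of the cut-point.** With N = 200, the sample median falls at population percentile 0.5 ± 1.96 × 0.5/√200, roughly the 43rd to the 57th.

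**The case against.** The strongest reply is that 9.5 states a grouping, not a test. With no endpoint, model or hypothesis named, the list may be meant for descriptive tables, with detail left to the SAP. This stands in part: the power figures describe what a test on these groups would achieve, not a test the plan commits to. But the grouping is the only specification given and no continuous analysis supplements it, so an SAP that follows 9.5 would carry it forward.

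The slopes are also illustrative, and the larger ones are generous. Section 1.2.2 can be read as putting the maximal LDL-C response at −67%. On that reading a slope of 10 around −53.4 passes the maximum at (67 − 53.4)/10 = 1.36 SD. At a slope of 5 both methods are weak and the gap is about 8 percentage points of power. This stands.

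Ten interaction tests also raise multiplicity: if independent, the chance of at least one false positive is 1 − 0.95^10 = 40%. That applies equally to ten tests on split markers, but it means any replacement needs an exploratory label.

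Stronger readings that a reader might infer are not supported:

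- *More than a third of the sample is thrown away.* Every subject is analysed. What is lost is information on a linear trend, and 36% is conditional on a normal marker; the documents give no marker distributions.
- *The cut-points are useless to others.* A reported median can be applied elsewhere. The limitation is that it is not fixed in advance.
- *The plan splits on post-treatment values.* The same list marks its LDL-C subgroup explicitly as post-baseline, so the unmarked levels are most naturally read as baseline. The missing word calls for clarification and is not evidence of a biased comparison.
- *The split has no benefit.* It is easy to display and does not assume linearity.

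**Conclusion.** The point holds as a matter of efficiency in exploratory analyses. Section 9.5 fixes a median grouping for nine markers and CD4+ count, and no other section examines them on a continuous scale as effect modifiers. For roughly normal markers and roughly linear modification, the split keeps about 64% of the information on the trend. At N = 180 and SD 25 it costs about 8 percentage points of power at a slope of 5 points per SD, 17 at a slope of 8 and 20 at a slope of 10. These figures rest on assumed slopes, normality and linearity, and the loss ranges from zero (step at the median) to more than half (strongly skewed marker, effect linear in the raw value). Even the continuous analysis has limited power for modest slopes, so the change improves these analyses without making them confirmatory.

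**What to change.** In section 9.5, and in the SAP that implements it:

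1. For each of the nine markers and CD4+ count, specify a treatment-by-baseline-marker interaction in the planned MMRM for percent change in LDL-C at week 12. Keep the marker continuous, log-transformed where skewed.
2. Report the slope difference with its 95% CI, and the estimated treatment effect at the 25th and 75th percentiles of the marker.
3. Keep the median-split tables for display only.
4. State that marker and CD4+ levels are baseline values.
5. Label the ten interaction analyses exploratory, without multiplicity control.

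The cost is a change of wording, with no new data, visits or subjects. The small downside is the assumption of an approximately linear trend on the chosen scale, which a spline can check.
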